**Novo Nordisk**

### **13.2 Case report form flow**

The investigator must ensure that data is recorded in the eCRF as soon as possible, preferably within 5 days after the visit. Once data has been entered, it will be available to Novo Nordisk for data verification and validation purposes.

Site specific eCRF data (in an electronic readable format) will be provided to the trial site before access to the eCRF is revoked. This data must be retained at the trial site.

Protocol: Liraglutide  
Trial ID: NN8022-4179  
UTN: U1111-1162-7884  
EudraCT no.: 2014-004415-37

**CONFIDENTIAL**

Date: 16 July 2020  
Version: 5.0  
Status: Final  
Page: 85 of 125

**Novo Nordisk**

## 14 Monitoring procedures

During the course of the trial, the monitor will visit the trial site to ensure that the protocol is adhered to, that all issues have been recorded, to perform source data verification and to monitor drug accountability. The first monitoring visit will be performed as soon as possible after FPFV at the trial site and no later than 4 weeks after. The monitoring visit intervals will depend on the outcome of the remote monitoring of the CRFs, the trial site's recruitment rate and the compliance of the trial site to the protocol and GCP, but will not exceed 12 weeks for trial sites with active subjects (defined as subjects in screening, treatment, or follow-up).

The monitor must be given direct access to source documents (original documents, data and records). Direct access includes permission to examine, analyse, verify and reproduce any record(s) and report(s) that are important to the evaluation of the trial. If the electronic medical record does not have a visible audit trail, the investigator must provide the monitor with signed and dated printouts. In addition the relevant trial site staff should be available for discussions at monitoring visits and between monitoring visits (e.g. by telephone).

All data must be verifiable in source documentation other than the CRF.

For all data recorded the source document must be defined in a source document agreement at each trial site. There must only be one source defined at any time for any data element.

The investigator must make a reasonable effort to obtain additional information from external sources e.g. primary physician and other hospitals/departments to collect information required to evaluate all inclusion and exclusion criteria if not available in the subject's medical record at the trial site and if not part of the screening assessments performed.

Considering the electronic source data environment, it is accepted that the earliest practically retainable record should be considered as the location of the source data and therefore transcription to the diary from the glucometer is considered the source document for recordings of glucometer.

Source data generated by the trial site can be corrected by another person than the person entering the source data if accepted by local regulations; any correction must be explained, signed and dated by the person making the correction.

The original diaries and PROs must not be removed from the trial site, unless they form part of the CRF and a copy is kept at the site.

The monitor will ensure that the CRFs are completed.

The following data will be source data verified for screening failures:

Protocol: Liraglutide  
Trial ID: NN8022-4179  
UTN: U1111-1162-7884  
EudraCT no.: 2014-004415-37

~~CONFIDENTIAL~~

Date: 16 July 2020  
Version: 5.0  
Status: Final  
Page: 86 of 125

**Novo Nordisk**

- Date for obtaining informed consent.
- Screen failure reason.
- SAEs

Monitors must review the subject's medical records and other source data to ensure consistency and/or identify omissions compared to the CRF. If discrepancies are found, the investigator must be questioned about these.

A follow-up letter (paper or electronic) will be sent to the investigator following each monitoring visit. This should address any action to be taken.

Protocol: Liraglutide  
Trial ID: NN8022-4179  
UTN: U1111-1162-7884  
EudraCT no.: 2014-004415-37

~~CONFIDENTIAL~~

Date: 16 July 2020  
Version: 5.0  
Status: Final  
Page: 87 of 125

**Novo Nordisk**

## 15 Data management

Data management is the responsibility of Novo Nordisk. Data management may be delegated under an agreement of transfer of responsibilities to a contract research organisation (CRO).

Appropriate measures, including encryption of data files containing person identifiable data, will be used to ensure confidentiality of subject data, when they are transmitted over open networks.

Data from central laboratories will be transferred electronically. In cases where data is transferred via non-secure electronic networks, data will be encrypted during transfer.

The subject and any biological material obtained from the subject will be identified by subject number and trial ID. Appropriate measures such as encryption or leaving out certain identifiers will be enforced to protect the identity of subjects in all presentations and publications as required by local, regional and national requirements.

Protocol: Liraglutide  
Trial ID: NN8022-4179  
UTN: U1111-1162-7884  
EudraCT no.: 2014-004415-37

~~CONFIDENTIAL~~

Date: 16 July 2020  
Version: 5.0  
Status: Final  
Page: 88 of 125

**Novo Nordisk**

## 16 Computerised systems

Novo Nordisk will capture and process clinical data using computerised systems that are described in Novo Nordisk Standard Operating Procedures and IT architecture documentation. The use and control of these systems are documented.

Investigators working on the trial may use their own electronic systems to capture source data.

Protocol: Liraglutide  
Trial ID: NN8022-4179  
UTN: U1111-1162-7884  
EudraCT no.: 2014-004415-37

CONFIDENTIAL

Date: 16 July 2020  
Version: 5.0  
Status: Final  
Page: 89 of 125

Novo Nordisk

## 17 Statistical considerations

If necessary, a statistical analysis plan (SAP) may be written in addition to the protocol, including a more technical and detailed elaboration of the statistical analyses.

Results from the statistical analysis will generally be presented by two-sided confidence intervals (CIs) with a confidence level of 95%. Superiority will be claimed if the two-sided p-value is less than 5% and the treatment estimate favours liraglutide.

The full analysis set (FAS) will be used in the analysis of the efficacy endpoints. For the safety endpoints, the safety analysis set (SAS) will be used. The definition of the analysis sets is given in Section [17.2](#).

For safety endpoints, summaries will be presented separately for the periods “in trial” and “on treatment” as defined in Section [17.4.1.2](#).

The baseline value will be defined as the last measured and available value from V3 (randomisation) and V2 (screening).

Laboratory values below the lower limit of quantification (LLOQ) will be set to  $\frac{1}{2}$ LLOQ.

### 17.1 Sample size calculation

This is a superiority trial comparing liraglutide to placebo. Based on previous experience the treatment effect after 52 weeks is expected to be considerable larger than after 16 weeks. Therefore the sample size calculation below focuses alone on the first co-primary endpoint.

It is difficult to assess the anticipated effect of liraglutide in BMI SDS in children and adolescents with PWS. It is anticipated that the effect is similar to the effect for adults.

The standard deviation (SD) is assessed based on publications and trial NN8022-3967 in adolescents with obesity aged 12–17 years. For the sample size scenarios, SDs of 0.15, 0.25 and 0.35 were investigated.

The effect of withdrawals is accounted for as a reduction of the anticipated treatment difference and increase of the SD. Since a conservative imputation method is planned for the main analysis of the primary endpoint, it is assumed that withdrawn subjects respond as if treated with placebo for the entire trial. The assumed withdrawal percentage at week 16 is 10% and 20% at week 52. This is lower than what was seen for trial NN8022-1839 in adults with obesity and adults with overweight. Since patients with Prader-Willi Syndrome are under close supervision by parents or institutional staff and for the lack of other therapeutic options, this assumption is considered reasonable. Let  $p_{WD}$  denote the probability of withdrawal. The adjustment for withdrawals is made by correcting the treatment difference  $\Delta$  and variance  $\sigma^2$  as

Protocol: Liraglutide  
 Trial ID: NN8022-4179  
 UTN: U1111-1162-7884  
 EudraCT no.: 2014-004415-37

~~CONFIDENTIAL~~

Date:  
 Version:  
 Status:  
 Page:

16 July 2020  
 5.0  
 Final  
 90 of 125

**Novo Nordisk**

$$\Delta_{corr} = (1 - p_{WD})\Delta$$

$$\sigma_{corr}^2 = \sigma^2 + \frac{2}{3}p_{WD}(1 - p_{WD})\Delta^2$$

The total number of subjects is shown for the investigated scenarios in the table below for 80%, 85% and 90% power.

**Table 17–1 Sample size calculations for different scenarios; total number of subjects**

Power	Treatment difference (completers)	SD		
		0.15	0.25	0.35
80%	-0.22	27	63	117
	-0.225	27	60	111
	-0.23	24	57	108
85%	-0.22	30	72	132
	-0.225	30	69	126
	-0.23	27	66	123
90%	-0.22	33	81	156
	-0.225	33	78	147
	-0.23	33	75	141

It seems realistic and conservative to assume a SD of 0.25 and a withdrawal rate of 10% after 16 weeks and 20% after 52 weeks. A withdrawal rate of 10% gives 57 subjects randomised. With this setting, a treatment difference of -0.23 corresponding to approximately a 5-6% decrease in BMI can be detected with a power of 80%. Assuming a withdrawal rate at 20% at week 52 a trial completion of 45 subjects, which is a regulatory requirement, is obtainable.

The distribution of the 57 subjects for randomisation on part A and B and the two treatment groups are shown in the table below.

Protocol: Liraglutide  
 Trial ID: NN8022-4179  
 UTN: U1111-1162-7884  
 EudraCT no.: 2014-004415-37

~~CONFIDENTIAL~~

Date: 16 July 2020  
 Version: 5.0  
 Status: Final  
 Page: 91 of 125

**Novo Nordisk**

**Table 17–2 Overview of randomised subjects**

	Liraglutide	Placebo	Total Liraglutide and Placebo	Expected number of subjects to complete treatment (at least 80%)	Minimum PIP requirement of subjects to complete treatment
Part A	22	11	33	28	28
Part B	16	8	24	19	17
Total	38	19	57	47	45

**17.2 Definition of analysis sets**

The following analysis sets are defined in accordance with the ICH-E9 guideline.

FAS: Includes all randomised subjects who have received at least one dose of trial product and have any post-randomisation data. The statistical evaluation of the FAS will follow the intention-to-treat (ITT) principle and subjects will contribute to the evaluation “as randomised”.

SAS: Includes all subjects exposed to at least one dose of trial product. Subjects in the SAS will contribute to the evaluation “as treated”.

Data from nominal visits (V10x and V19x) will be used prior to imputation of remaining missing data unless otherwise stated.

Before data are locked for statistical analysis, a blind review of all data will take place. Any decision to exclude a subject or single observations from the statistical analysis is the joint responsibility of the trial statistician, the ITM and the medical specialist. Exclusion of data from analyses will be used restrictively and normally no data should be excluded from the FAS. The subjects or observations to be excluded, and the reasons for their exclusion must be documented and signed by those responsible before database lock. The subjects and observations excluded from analysis sets, and the reason for this, will be described in the clinical trial report.

**17.3 Primary endpoints**

The two co-primary endpoints are:

Protocol: Liraglutide  
Trial ID: NN8022-4179  
UTN: U1111-1162-7884  
EudraCT no.: 2014-004415-37

CONFIDENTIAL

Date: 16 July 2020  
Version: 5.0  
Status: Final  
Page: 92 of 125

Novo Nordisk

- Change from baseline in BMI SDS after 16 weeks of treatment
- Change from baseline in BMI SDS after 52 weeks of treatment

The hypotheses of equality between liraglutide and placebo for each of the two endpoints are tested in a hierarchical manner in the order in which the endpoints are presented. The implication is that liraglutide will only be considered statistically significantly better than placebo at 52 weeks if it is considered statistically significantly better with respect to the first primary endpoint.

The primary analysis will include subjects from all strata, i.e. both from part A and part B (provided that the external DMC recommends that part B will be conducted).

BMI SDS will be summarised using descriptive statistics according to the stratification factor for Tanner stage and stratification factor for glycaemic category. In case there are a very low number of subjects within one glycaemic category, the description may be done according to stratification factor for Tanner stage alone.

The analysis of each of the co-primary endpoints will use the same approach and is described below.

The objective is to show that liraglutide is superior to placebo in obtaining weight loss.

Let  $\mu_{\text{liraglutide}}$  and  $\mu_{\text{placebo}}$  denote mean change in BMI SDS for liraglutide and placebo respectively. The null-hypothesis and the alternative hypothesis are:

$H_0: \mu_{\text{liraglutide}} = \mu_{\text{placebo}}$  against the alternative  $H_A: \mu_{\text{liraglutide}} \neq \mu_{\text{placebo}}$

The null-hypothesis will be rejected on a 5% level if the two-sided 95% confidence interval of the treatment difference  $\mu_{\text{liraglutide}} - \mu_{\text{placebo}}$  excludes 0. If the upper limit is below 0 superiority of liraglutide against placebo can be concluded.

The hypothesis will be tested using an analysis of covariance (ANCOVA) with treatment, sex, region, baseline glycaemic category, stratification factor for Tanner stage and interaction between baseline glycaemic category and stratification factor for Tanner stage as fixed effects and baseline BMI SDS and baseline age as covariates. Part A of the trial includes Tanner stage 2-5 or hormonally-induced puberty, and part B includes Tanner stage below 2 and subjects with premature adrenarche. The stratification factor for Tanner stage includes three levels; stage below 2 (defined as Tanner stage 1 with or without premature adrenarche) (corresponding to part B), stage 2 and 3 together, and stage 4 and 5 together (the last two corresponds to part A). The baseline glycaemic category includes two levels; presence and absence of dysglycaemia.

Missing data will in the main analysis be handled by the following multiple imputation (MI) method. A pattern mixture model approach is applied where withdrawn subjects with missing

Protocol: Liraglutide  
 Trial ID: NN8022-4179  
 UTN: U1111-1162-7884  
 EudraCT no.: 2014-004415-37

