**Novo Nordisk**

## 4 Objectives and endpoints

### 4.1 Objectives

#### Primary objective

To compare the efficacy of liraglutide versus placebo on weight loss in paediatric subjects with obesity and PWS at 16 weeks and versus no treatment at 52 weeks.

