Subjects will be randomised 2:1 to receive liraglutide or liraglutide placebo. Part A has four strata as subjects are stratified according to Tanner stage 2–3 and 4–5 and by presence/absence of dysglycaemia. Part B includes subjects with Tanner below 2 (defined as Tanner stage 1 with or without premature adrenarche) and has two strata for presence/absence of dysglycaemia, see section [11](#).

Dysglycaemia is defined as pre-diabetes with FPG 5.6 – 6.9 mmol/L (both inclusive) (100-125 mg/dL) (both inclusive) and/or HbA1c 5.7 – 6.4 % (both inclusive). The HbA1c and FPG results from V2 must be used.

At least 30% of subjects will be from areas with lifestyle and nutrition comparable to that in the European Union (EU). All subjects and/or their legally acceptable representative (LAR) will undergo counselling for weight loss and must be prescribed a structured programme for diet and physical activity throughout the trial (from randomisation to the end of the trial). Placebo injections will be stopped at week 16, at the end of the double-blind period.

Subjects treated with growth hormone therapy may enter the trial and will have no change in treatment plan with growth hormone from randomisation to the end of the open-label period (subjects on growth hormone will stay on, and subjects off growth hormone will stay off during this period. Adjustments to doses of growth hormone are permitted).

Protocol: Liraglutide  
Trial ID: NN8022-4179  
UTN: U1111-1162-7884  
EudraCT no.: 2014-004415-37

~~CONFIDENTIAL~~

Date: 16 July 2020  
Version: 5.0  
Status: Final  
Page: 30 of 125

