**Novo Nordisk**

## 5.2 Rationale for trial design

This trial is designed in accordance with regulatory requirements (FDA 21 CFR 314.126) and recommendations from the literature.

The design has been chosen in accordance with the trial objectives and with input from the Paediatric Committee (PDCO) of the European Medicines Agency's (EMA).

The co-primary efficacy endpoints are change in BMI SDS from baseline to 16 weeks and 52 weeks. Change in BMI SDS is selected based on the EMA recommendation regarding the assessment of efficacy of new medicinal products for the treatment of obesity in children. The first 16 weeks will be placebo-controlled and double-blinded to evaluate the effect of liraglutide versus placebo, as an adjunct to a structured program for diet and physical activity. The 36-week open-label period will provide supportive evidence to evaluate the continued efficacy and safety of liraglutide. Placebo injections will be stopped at the end of the double-blind period to avoid inconvenience to the subjects.

The rationale for choosing a treatment duration of 16 weeks for the primary efficacy endpoint is that this time period is considered adequate to show effect of liraglutide treatments on the endpoint, and to minimise the duration of placebo injections. The 36-week open-label period will allow additional time to evaluate the full effect of liraglutide on other efficacy endpoints including BMI, body weight, waist to hip circumference, cardiovascular risk factors (hsCRP and lipid profile), blood pressure and glucose metabolism and safety assessments. Furthermore, a 52-week total trial period is regarded to be sufficient to characterise the safety and tolerability profiles of liraglutide.

A 2:1 randomisation was chosen to ensure more subjects will receive active treatment with limited number of subjects enrolled in the trial, and therefore more safety data on liraglutide treatment is obtained.

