## 11 Randomisation procedure and breaking of blinded codes

Randomisation will be stratified according to pubertal status and by presence/absence of dysglycaemia. Stratification will be controlled by the IV/WRS. The stratification factors are:

Pubertal status:

- Tanner below 2 (defined as Tanner stage 1 with or without premature adrenarche) (part B only)
- Tanner 2 or 3 (part A only)
- Tanner 4 or 5 (part A only)

Glycaemic status:

- dysglycaemia yes
- dysglycaemia no

Dysglycaemia is defined as pre-diabetes with FPG 5.6 – 6.9 mmol/L (both inclusive) (100 - 125 mg/dL) (both inclusive) and/or HbA1c 5.7 – 6.4 % (both inclusive). The HbA1c and FPG results from V2 must be used.

At randomisation, the subjects will be randomised to one of two parallel treatment groups: liraglutide or placebo. The randomisation will be carried out in a 2:1 manner using the IV/WRS.

The trial is a double-blind trial for the first 16 weeks followed by a 36 weeks open-label treatment period. Only subjects treated with liraglutide will receive trial treatment in the 36-weeks open-label treatment period. The subject's treatment allocation will be un-blinded on an on-going basis after the double blind period at week 16 (V10).

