## 2 Statistical hypotheses

The two co-primary endpoints are:

- Change from baseline in BMI SDS after 16 weeks of treatment
- Change from baseline in BMI SDS after 52 weeks of treatment

The hypotheses of equality between liraglutide and placebo for each of the two endpoints are tested in a hierarchical manner in the order in which the endpoints are presented. The implication is that liraglutide will only be considered statistically significantly better than placebo at 52 weeks if it is considered statistically significantly better with respect to the first primary endpoint.

The primary analysis will include subjects from all strata, i.e. both from part A and part B (provided that the external DMC recommends that part B will be conducted).

BMI SDS will be summarised using descriptive statistics according to the stratification factor for Tanner stage and stratification factor for glycaemic category. In case there are a very low number of subjects within one glycaemic category, the description may be done according to stratification factor for Tanner stage alone.

The analysis of each of the co-primary endpoints will use the same approach and is described below.

The objective is to show that liraglutide is superior to placebo in obtaining weight loss.

Let  $\mu_{\text{liraglutide}}$  and  $\mu_{\text{placebo}}$  denote mean change in BMI SDS for liraglutide and placebo respectively. The null-hypothesis and the alternative hypothesis are:

$H_0: \mu_{\text{liraglutide}} = \mu_{\text{placebo}}$  against the alternative  $H_A: \mu_{\text{liraglutide}} \neq \mu_{\text{placebo}}$

The null-hypothesis will be rejected on a 5% level if the two-sided 95% confidence interval of the treatment difference  $\mu_{\text{liraglutide}} - \mu_{\text{placebo}}$  excludes 0. If the upper limit is below 0 superiority of liraglutide against placebo can be concluded.

Statistical Analysis Plan  
Trial ID: NN8022-4179  
UTN: U1111-1162-7884  
EudraCT No: 2014-004415-37

~~CONFIDENTIAL~~

Date:	14 December 2020	Novo Nordisk
Version:	1.0	
Status:	Final	
Page:	9 of 36	

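### The week-52 co-primary conclusion is worded as superiority over placebo, but the stated comparator at week 52 is no treatment, and placebo and blinding both end at week 16

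*Protocol*

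**What the plan says.** The primary objective (Protocol sections 1 and 4.1, SAP section 1.1.1) names two comparators. Liraglutide is compared with placebo in paediatric subjects "with obesity and PWS at 16 weeks and versus no treatment at 52 weeks".

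The hypothesis text does not keep that distinction. Protocol section 17.3 introduces it with "The analysis of each of the co-primary endpoints will use the same approach and is described below", uses a single placebo mean in the null and alternative hypotheses, and states that "liraglutide will only be considered statistically significantly better than placebo at 52 weeks if it is considered statistically significantly better" on the week-16 endpoint. SAP section 2 repeats this and closes with "If the upper limit is below 0 superiority of liraglutide against placebo can be concluded", naming no time point. SAP section 5.1 carries the same closing sentence under its general considerations.

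On design, Protocol section 5.1 says "Placebo injections will be stopped at week 16, at the end of the double-blind period". Section 11 unblinds each subject's allocation at V10 (week 16) and gives open-label trial treatment to the liraglutide arm only. SAP Table 4-2 ends on-treatment time for placebo at week 16. On the role of the later period, Protocol section 5.2 says "The 36-week open-label period will provide supportive evidence to evaluate the continued efficacy and safety of liraglutide", while the same section lists the week-52 endpoint as co-primary.

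**The concern.** A confirmatory conclusion should name the comparison that the data contain. At week 52 the control arm has had no injections for 36 weeks, and investigator and subject know the allocation. The contrast therefore combines any drug effect with any effect of continuing injections against having none and of knowing the arm. A concurrent blinded placebo would separate these, but there is none after week 16.

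Under the plan's own rule, a significant week-52 result would be reported as superiority over placebo. That departs from the sponsor's stated objective and claims more than the design can attribute to the drug. SAP Appendix 2, which lists changes to the protocol's planned analyses, does not correct it. The design rationale adds to the confusion by calling supportive a period whose endpoint is tested as co-primary.

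**Working it through.** **1. The passages side by side**

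- Comparator in the objective: placebo at week 16, no treatment at week 52 (Protocol 4.1, SAP 1.1.1).
- Comparator in the hypotheses and decision rule: placebo at both weeks (Protocol 17.3, SAP 2; SAP 5.1 with no time point).
- Treatment received by the control arm: placebo in weeks 0 to 16, none in weeks 16 to 52 (Protocol 5.1, 5.3 and 11; SAP Table 4-2).
- Blinding: kept to week 16. Flow chart footnote 2 requires V10 assessments before the dispensing session that reveals the allocation, so the week-16 comparison is protected. The week-52 comparison is not.

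Part of the comparison period without placebo or blind: 52 − 16 = 36 weeks, and 36/52 = 69%. This is a share of calendar time, not a measure of bias.

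**2. Does the sample size depend on the wording?**

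Inputs from Protocol 17.1 and Table 17-1: difference 0.23 in absolute value, SD 0.25, withdrawal 10%, power 80%. Two-sided 5% and 2:1 allocation are as planned.

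- Corrected difference: (1 − 0.10) × 0.23 = 0.207.
- Corrected variance: 0.25² + (2/3)(0.10)(0.90)(0.23²) = 0.0625 + 0.0032 = 0.0657, so SD = 0.2563.
- Two-sample comparison, 2:1, noncentral t: the smallest total that reaches 80% is 57 (38 v 19), with power 80.6%.

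This reproduces the protocol's 57, and the same method reproduces all 27 cells of Table 17-1. Section 17.1 sizes the week-16 endpoint alone. Renaming the week-52 comparator changes none of these figures.

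**3. What the 5% test protects at week 52**

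The documents give no value for an open-label effect, so this step rests on an assumed quantity. Let b be a week-52 difference in mean BMI SDS change, in liraglutide's favour, that arises only from known allocation or from having no injections. Suppose no drug effect, SD 0.25, 38 v 19 subjects, complete data and an unadjusted t test on 55 degrees of freedom.

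- Standard error: 0.25 × √(1/19 + 1/38) = 0.070.
- Chance that the upper 95% limit falls below 0, from the noncentral t distribution with noncentrality b/SE:

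| assumed b | chance of a superiority conclusion |
|---|---|
| 0 | 2.5% |
| 0.025 | 5.4% |
| 0.05 | 10.4% |
| 0.10 | 28.7% |

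Read as liraglutide against no treatment, open-label, b is part of the contrast being tested and the error rate holds. Read as liraglutide against placebo, the error rate holds only if b = 0. If b ran the other way, the chance would fall below 2.5%.

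**The case against.** The strongest reply is that placebo is an arm label. Section 11 names the two randomised groups as liraglutide and placebo, section 8.1.10 refers to the placebo group during the open-label period, SAP Table 4-2 defines an open-label period for placebo, and subjects are analysed as randomised. On that reading the placebo mean is the mean of the arm randomised to placebo, which is a proper parameter at both weeks. The objective is worded correctly, and section 17.3 describes the estimate as the effect of liraglutide added to diet and activity counselling, which suits an untreated control. Stopping placebo was also a reasoned choice, made with Paediatric Committee input to spare subjects the injections.

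Most of this stands. It shows that the parameter and the test are sound. It does not settle the conclusion, because 17.3 and SAP 2 put placebo into the claim itself, where it departs from the objective.

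Stronger readings are tempting but are not supported:

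- A reader might infer that the placebo conclusion is written into every week-52 secondary endpoint. Protocol 17.4.1.1 and SAP 5.4.1.1 carry over the statistical method and speak of treatment differences. Only the general sentence in SAP 5.1 reaches further.
- A reader might infer unequal follow-up. The flow chart keeps V11 to V19, with body weight and counselling, for both arms. Dispensing, drug accountability, IV/WRS sessions and pen training are limited to liraglutide, and optional home visits to the placebo arm.
- A reader might infer a known bias through unblinded dietitians or disappointed families. The documents state neither, the direction of any change in behaviour is unknown, and BMI SDS comes from measured weight and height.
- A reader might conclude that hyperphagia efficacy should rest on the week-16 score alone. That would be a preference; nothing in the documents requires it.

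**Conclusion.** The inconsistency holds and the text is wrong as written. For week 52, Protocol 17.3 and SAP 2, together with the undated sentence in SAP 5.1, allow a conclusion of superiority over placebo that neither the objective nor the design supports. It affects one of the two co-primary conclusions.

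The week-52 contrast remains a valid randomised comparison of continued liraglutide with the arm whose placebo injections stopped at week 16, made open-label. The planned 57 subjects, the two-sided 5% level and the fixed test order all stand. It would be wrong to infer that the week-52 test is invalid or that a biased result has been shown. The 69% describes exposure to open-label conditions only, and the error rates above 2.5% depend entirely on assumed values of b.

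**What to change.** In Protocol 17.3 and SAP 2, write two hypotheses:

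- H01: week 16, liraglutide v placebo, double-blind.
- H02: week 52, liraglutide v the arm randomised to placebo and untreated since week 16, open-label, tested only if H01 is rejected.

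In Protocol 17.3, SAP 2 and SAP 5.1, limit the conclusion of superiority over placebo to week 16. Word the week-52 conclusion as superiority over no treatment (open-label), and label the week-52 comparator to match in tables and figures. In Protocol 5.2, reconcile the supportive role given to the open-label period with the co-primary status of week 52.

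The cost is editing text and output labels. No data collection, sample size, model or test order changes. The downside for the sponsor is a narrower week-52 claim.
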